Muscle relaxation will be maintained by 0.1mg/kg/30 minute of Atracrurium.

- Mechanical ventilation will be adjusted with fresh gas flow oxygen in air 30-50% at a rate of 1 L min⁻¹to maintain end-tidal carbon dioxide of 35-40 mm Hg and Spo2 greater than 94%.
- BIS values will be maintained between 40 and 60.
- All surgical procedures will be done in the range between 10 am and 1 pm and by the same surgical team.
- Patients hemodynamic parameters regarding blood pressure and heart rate will be recorded every 2.5 minutes.
- Core temperature will be measured using an esophageal thermometer and normothermia will be maintained using a forced air warming blanket and actively warmed infused solution.
- Patients will receive ringer solution infusion at a rate 2 5 ml / kg / hour.
- Patients were randomly allocated to one of three groups namely the control group (Group C), the field block group (Group FB), or the RSB group (Group RSB) according to a computer generated randomization table (research randomizer, https://www.randomizer.org). Patients in the Field block group received a sham bilateral RSB using a total volume of 0.3ml. kg⁻¹ of normal

saline plus a field block using 0.3ml. kg⁻¹ of 0.5% bupivacaine. The RSB group received a bilateral RSB using a total volume of 0.3ml. kg⁻¹ of 0.5 % bupivacaine plus a sham field block using 0.3 ml. kg⁻¹ of normal saline. The control group received 0.3 ml. kg⁻¹ of normal saline for each block. A colleague not participating in the trial prepared the syringes that were used for the blocks. The patients, the anaesthetist administering the blocks, and colleagues collecting the postoperative observations were not aware of group allocation or injectate composition.

- An increase in HR and/or MAP > 25 % of baseline values will be treated by IV fentanyl 0.5 μg kg⁻¹ boluses & the total fentanyl dose will be recorded. Atropine 0.5 mg increments will be used to control bradycardia (<50 beat min⁻¹) while hypotension (less than 20% of preanesthetic level) will be managed by increasing fluid infusion rate or decreasing inhalational anesthetic concentration.
- Reversal of neuromuscular blockade will be achieved by intravenous administration of neostigmine 0.05 mg kg⁻¹ and atropine 0.02 mg kg⁻¹.
- Patients will be extubated and transferred to post- anesthetic care unit.
- Postoperatively, pain was controlled using morphine PCA, paracetamol 1 gm intravenously every 6 hours and Diclofenac intravenously every 12 hours.

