- VAS will be recorded immediately post-operative, after 2, 4 and 6 hours.
- Time to first analgesia requirement will be recorded and 24 hour postoperative morphine consumption will be recorded.
- Nausea and vomiting will be recorded immediately postoperative using a categorical scoring system (0 = none, 1 = nausea, 2 = retching, 3 = vomiting).
 Ondansteron 4 8 mg i.v will be given for patients with score 2.

Research Template 6 Final Version: 14/11/2011

• Pa	atients will be discharged out after sco	ring 12 points or more according to Fast
tra	ack discharge score (5) as follows:	
>	Level of consciousness	Score
	Awake and oriented	2
	Arousal with minimal stimulation	1
	Responsive only to tactile stimulation	n 0
>	Physical activity	
	Able to move all extremities on	
	command	2
	Some weakness in movement of	
	extremities	1
	Unable to voluntarily move extremiti	ies 0
>	Hemodynamic stability	
	Blood pressure less than 15% of baseline	
	MAP value	2
	Blood pressure 15%–30% of baseline	
	MAP value	1
	Blood pressure more than 30% below	
	baseline MAP value	0
>	Respiratory stability	
	Able to breathe deeply	2
	Tachypnea with good cough	1
	Dyspneic with weak cough	0
>	Oxygen saturation status Maintains value more than 90% on	

	noom oir	2
	room air	2
	Requires supplemental oxygen (nasal	
	prongs)	1
	Saturation less than 90% with	
	supplemental oxygen	0
>	Postoperative pain assessment	
	None or mild discomfort	2
	Moderate to severe pain controlled with	
	IV analgesics	1
	Persistent severe pain	0
>	Postoperative emetic symptoms	
	None or mild nausea with no active	
	vomiting	2
	Transient vomiting or retching	1
	Persistent moderate to severe nausea	
	and vomiting	0
Total sco	ore 14	

Total Score 14

Sampling:

Patients in the three groups will undergo blood sampling for measurement of cortisol and catecholamine level using ELISA technique 3 times :

- 30 min. pre –op.
- 1 hour after the start of the procedure.

- 2 hour after the end of the procedure.
- 6 hours after the end of the procedure

Pain assessment:

Pain score to surgery will be assessed according to the VAS pain score sheet as follows:

- Immediately after the admission to recovery room.
- 15 minutes following the admission to recovery room.
- 2 hours after the end of the procedure.
- 6 hours after the end of the procedure.
- Time to 1st analgesia request.
- 24 hour post operative analgesia requirement.
- Intra-operative fentanyl consumption.

Primary outcomes (Most important outcomes to be assessed):

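### The printed discharge rule (12 or more out of 14, no item minimum) clears a patient who scores 0 on one item, such as persistent severe pain, if the other six items score 2

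*Combined protocol and SAP*

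**What the plan says.** The rule is in the postoperative part of Methodology in details in the combined protocol and SAP. Patients leave on "ring 12 points or more according to Fast" track discharge score, which is cited to reference 5. The table has seven items: consciousness, physical activity, haemodynamic stability, respiratory stability, oxygen saturation, pain and emetic symptoms. Each is scored 0, 1 or 2, and the printed maximum is 14.

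The 0 grades that matter most here are:
- Pain: "Persistent severe pain". The grade above it, scored 1, is "Moderate to severe pain controlled with" intravenous analgesics.
- Haemodynamics: "Blood pressure more than 30% below" the baseline MAP value.
- Saturation: "Saturation less than 90% with" supplemental oxygen.

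During anaesthesia the protocol holds a tighter line. Under Induction and maintenance, "hypotension (less than 20% of preanesthetic level) will be managed by increasing fluid infusion rate" or by reducing the inhalational agent, and SpO2 is kept above 94%.

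No section sets a minimum for any single item. The modified Aldrete score is listed as a secondary outcome but without a threshold, so it does not supply one.

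**The concern.** A sum score with a cut-off lets good items compensate for a bad one. Here the cut-off sits two points below the maximum and each item spans two points, so one item can fail completely without blocking discharge.

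The stake is mainly safety. In a trial of analgesia, the rule allows a patient to move on while in uncontrolled severe pain. That case is believable in this population: ASA I or II, aged 18 to 60, elective surgery, so normal consciousness, movement, breathing and saturation can well accompany uncontrolled pain. One arm receives saline at both block sites, and the sample size section plans for a mean pain score of 7.1 in controls against 4.65 with the rectus sheath block. Those planning figures are not tied to the discharge item or to a time point, so they show only that substantial pain was expected in one arm.

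The primary pain comparison does not depend on the rule. The secondary outcome of time to leaving hospital would depend on it only if this score decides when patients leave hospital.

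**Working it through.** **Inputs (all from the score table and the sentence above it).** Seven items; each scored 0, 1 or 2; discharge if the total is 12 or more.

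**1. The printed maximum.** 7 × 2 = 14, which agrees with the table.

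**2. One item at 0.** Best possible total = 6 × 2 + 0 = 12, which meets the cut-off. If any further point is lost, the total is at most 11 and the patient fails. With two items at 0 the best total is 5 × 2 = 10, also a fail. So a passing patient can have at most one 0, and then only with all six other items at 2.

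**3. Full count.** There are 3^7 = 2,187 patterns. Those with a total of 12 or more are:

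| Pattern | Total | Number |
|---|---|---|
| All items at 2 | 14 | 1 |
| One item at 1, the rest at 2 | 13 | 7 |
| Two items at 1, the rest at 2 | 12 | (7 × 6)/2 = 21 |
| One item at 0, the rest at 2 | 12 | 7 |
| **Sum** | | **36** |

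For any given item there are 3^6 = 729 patterns with that item at 0, and exactly 1 of them passes.

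**4. Two possible remedies compared.**
- Total of 12 or more and no item at 0: 36 − 7 = 29 patterns remain. Only the 7 unwanted ones go.
- Cut-off raised to 13: 1 + 7 = 8 patterns remain. The 7 unwanted ones go, but so do the 21 patterns with two items at 1 and none at 0.

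**5. Blood pressure illustration.** Assumptions: baseline MAP of 80 to 100 mmHg (not given in the documents), and the intraoperative hypotension wording read as a 20% fall in MAP from the pre-anaesthetic level.
- Treatment threshold during anaesthesia: 0.80 × 80 = 64 to 0.80 × 100 = 80 mmHg.
- Boundary for a score of 0 at discharge: 0.70 × 80 = 56 to 0.70 × 100 = 70 mmHg.

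A patient below 56 to 70 mmHg can therefore pass the discharge rule if all else scores 2, although intraoperative treatment would already have started below 64 to 80 mmHg.

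**The case against.** The arithmetic is not in dispute; the objections are about weight.

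- **The source may contain a floor.** The score is named and cited, and a site could apply it as published. Reference 5 is not available here, so this stays open. If the source has an item minimum, the protocol transcribed it incompletely and the correction is the same. If it has none, the gap is in the score as adopted.
- **The patient may only be leaving recovery.** This reading is at least as plausible as leaving hospital: "Patients will be extubated and transferred to post- anesthetic care unit", after which morphine PCA, regular intravenous paracetamol and diclofenac, pain scores and blood samples to 6 hours are planned, and "24 hour postoperative morphine consumption will be recorded". This reduces the harm, because severe pain would still have planned treatment. It does not remove it: a patient in persistent severe pain would still leave the more closely observed unit on the strength of a rule.
- **The physiological examples are narrow.** Saturation below 90% on oxygen would have to coexist with deep breathing and full alertness. An intraoperative blood pressure trigger and an awake recovery score also serve different purposes. Both points stand, which is why pain is the leading example.
- **No bias between groups is shown.** One rule applies to all arms and the observers are blinded. This stands; the point is one of safety and not of the primary inference.
- **Clinicians would hold such a patient back anyway.** Often they would, but the protocol should then say so.

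**Conclusion.** The concern holds. Followed exactly, the printed rule clears a patient at the worst grade of any one item provided the other six score 2: 7 of the 36 passing patterns, one per item. This needs no assumption beyond reading the table as printed. How often it would occur cannot be estimated, because the documents give no item-level frequencies, and pattern counts are not probabilities. The blood pressure figures rest on the assumed baseline and on the reading of the hypotension wording stated above; the conclusion does not depend on them.

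The sponsor should correct this on safety grounds. It does not touch the sample size, the primary outcome or its analysis. Any effect on time to hospital discharge is conditional on the score governing that step.

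**What to change.** Replace the condition with: a total of 12 or more with no item scored 0. This is preferable to raising the cut-off to 13, which would also turn away the 21 patterns with two mildly reduced items.

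The cost is one sentence in the protocol. A patient with a single 0 waits until that item improves by one step: moving it from 0 to 1 gives 12 + 1 = 13 with no zero, which meets the new rule. For pain, that step means control with intravenous analgesics, which the protocol already provides. The number of patients delayed, and for how long, cannot be estimated from the documents.

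Two inexpensive additions would help but are not needed for the correction: saying in the same sentence whether the rule governs leaving the recovery unit or the hospital, and recording the seven item scores with the time of each assessment, so that compliance with the floor can be verified.

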Comparison Between Ultra Sound Guided Rectus Sheath Block and Field Block for Midline Hernia Repair

NCT03225313

Start Date 20th August 2017

Investigators:

1. [name]

a. Other Investigators	[name]. [name].
	[name] [name]. [name] [name]. [name] [name]. [name]
c. Department name	Anesthesia Department.

Background and Rationale:

Pain is a complex but an important protective phenomenon. It may be defined as an unpleasant sensory and emotional experience associated with actual or potential tissue damage or described in terms of such damage (1). Good operative analgesia reduces the stress response to surgery, which is very important for patients with compromised cardiovascular respiratory functions (1). Good postoperative pain relief is important as it alleviates patient's distress and helps in rapid uncomplicated recovery (1).

Field block achieved by wound infiltration is a method of postoperative analysis commonly used alone or as a part of multimodal analysis regimens (2). It was developed to improve postoperative analysis, reduce opioid consumption and

hasten patient recovery .The use of local anesthetics (LAs) instead of opioid minimizes opioid adverse reactions, reduces nursing work, decreases resting pain, pain on motion, and thus allows better patient mobility (2). Field block carries the risk of wound infection and some surgeons oppose its use.

A rectus sheath block can provide effective pain relief for umbilical or other midline surgical incisions by blocking the intercostals nerves. It can be done using the landmark technique but it carries the risk of puncturing the posterior rectus sheath, peritoneum and bowel (3).

Use of ultrasound technology for rectus sheath block has reduced this risk considerably (3). Ultrasound guidance for regional anesthesia is associated with higher block success rates, shorter onset times, and reduced total anesthetic dose required and reduced complications. There is also the advantage of direct observation of pattern of anesthetic spread (4).

Objectives:

To compare between Ultra-sound guided rectus sheath block VS Field block infiltration in providing a good analgesia for patients undergoing midline hernia repair to detect which one is superior.

Study Design:

Prospective randomized double blinded controlled clinical trial will be done with a total number of 75 patients will be divided into 3 groups.

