Assessment of postoperative pain with each technique.

Secondary outcome parameters (other outcomes to be assessed) :

- Assessment of stress response with each technique through measuring cortisol and catecholamine levels.
- Hemodynamic Parameters regarding blood pressure and heart rate.
- Incidence of nausea and vomiting post operative.

- Modified Aldrete score.
- Time to hospital discharge.

STATISTICAL METHODS:

Sample size calculation was done using the comparison of postoperative pain score between RSB, local infiltration and control groups as it was the primary outcome of our study. As reported in previous publication (6,7) the mean \pm S.D. of postoperative pain score in RSB group was 4.65 ± 2.1 , while in local infiltration group it was 5.45 ± 1.9 and in control group it was 7.1 ± 1.1 . We calculated that a sample size of 23 in each group will be able to detect a one unit difference between the groups with 80% power at $\alpha = 0.05$ level using analysis of variance test (one way ANOVA test) for independent samples. The sample size calculation was done using the G*Power© software (Institut für Experimentelle Psychologie, Heinrich Heine Universität, Düsseldorf, Germany) version 3.1.9.2. To allow for drop-outs, 25 patients in each group were recruited.

The statistical analysis was performed using IBM SPSS® Statistics version 22 (IBM® Corp., Armonk, NY, USA). Numerical data were expressed as mean and standard deviation or median and range as appropriate. The qualitative data were expressed as frequency and percentage. The relation between qualitative variables was examined using either Pearson's Chi-square test or Fisher's exact test.

The quantitative continuous data were tested for normality using the Kolmogorov-Smirnov test and the Shapiro-Wilk test. The comparisons between the three groups were done using either analysis of variance (ANOVA) for normally distributed quantitative variables or Kruskal-Wallis test (non-parametric ANOVA) for none-normally distributed data then post-hoc test" was used for pair-wise comparison. ANOVA with repeated measures (for normally distributed data) or Friedman test (non-parametric ANOVA with repeated measures for non- normally distributed data) was used to compare more than two consecutive measures of numerical variables

followed by post hoc tests for pairwise comparisons of repeated readings. Due to multiple comparisons, the p-value was corrected using the Bonferroni method.

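### The objective is rectus sheath block versus field block, but the primary comparison is a three-group test including saline, and the pair that answers the objective is not designated as decisive

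*Combined protocol and SAP*

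**What the plan says.** - **Objectives.** The aim is "To compare between Ultra-sound guided rectus sheath block VS Field block infiltration", in order "to detect which one is superior". Saline is not mentioned.
- **Methodology in details.** The third arm is a double sham: "The control group received 0.3 ml. kg⁻¹ of normal saline for each block".
- **Primary outcomes.** "Assessment of postoperative pain with each technique". No contrast is named.
- **STATISTICAL METHODS, sample size.** The calculation uses the "comparison of postoperative pain score between RSB, local infiltration and control groups as it was the primary outcome of our study", by one-way ANOVA. Planning means (SD) are 4.65 (2.1) for RSB, 5.45 (1.9) for local infiltration and 7.1 (1.1) for control. The result is 23 per group for a one-unit difference with 80% power at 0.05, raised to 25 for drop-outs.
- **STATISTICAL METHODS, analysis.** Three groups are compared by ANOVA or Kruskal-Wallis; then an unnamed post-hoc test "was used for pair-wise comparison". A Bonferroni correction follows, without a stated scope. No sentence ranks the pairs, orders the tests, or says which result establishes superiority.

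**The concern.** The question has two groups and the comparison called primary has three. The three-group null hypothesis is false as soon as either block beats saline, so rejecting it does not show that the blocks differ. A report could present a significant primary test while the stated objective stays open.

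The pair that answers the objective sits among three post-hoc pairs, without priority and with a stricter threshold than a single primary comparison would need. Nor does the plan rule out a known misreading: one block differs significantly from saline, the other does not, and the first is called superior.

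**Working it through.** **Inputs.** Means, SDs, 25 per group and two-sided 0.05 come from STATISTICAL METHODS. Assumptions: one pain time point (several are listed and none is named primary), normal data, and Bonferroni over the three group pairs, 0.05/3 = 0.0167.

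**1. The plan's own figure.** For one-way ANOVA, f = (SD of the group means)/(within-group SD). Means one unit apart in steps (0, 1, 2) with SD 2.1 give f = 0.8165/2.1 = 0.389, which needs 23 per group (power 81.4%). So 23 can be reproduced for the three-group test, although the plan does not say which means and SD were entered. The cited means with pooled SD √[(2.1² + 1.9² + 1.1²)/3] = 1.754 give f = 1.020/1.754 = 0.582 and only 11 per group.

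**2. Where the three-group signal comes from.** The grand mean is 17.2/3 = 5.733. The squared deviations sum to 1.174 + 0.080 + 1.868 = 3.122. The RSB-FB part is 0.80²/2 = 0.32. The part for the average of the blocks against saline is 2.05² × 2/3 = 2.802. About 10% (0.32/3.122) of the signal concerns the objective; about 90% is block against saline.

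**3. Identical blocks.** Set both blocks to 5.05, the mean of 4.65 and 5.45, against 7.1 (difference 2.05). The SD of the means is 2.05 × √2/3 = 0.966. With common SD 2.1, f = 0.966/2.1 = 0.460 and the noncentrality is 75 × 0.460² = 15.9; power is about 95%. Simulation with the stated SDs gives 99.7%.

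**4. Power of the RSB-FB pair at 25 per arm.** The SD from those two groups is √[(2.1² + 1.9²)/2] = 2.00. The standard error is 2.00 × √(2/25) = 0.566. The noncentrality is 0.80/0.566 = 1.41, or 1.00/0.566 = 1.77.

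| True difference | Two-sided 0.05 | Two-sided 0.0167 |
|---|---|---|
| 0.80 | 28% | 15% |
| 1.00 | 41% | 25% |

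For 80% power at 0.05, this pair needs 100 per arm (0.80) or 64 per arm (one unit).

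**5. Which error term.** The three-group pooled SD (1.754) is pulled down by the control SD of 1.1 and understates the RSB-FB error (2.00). With the stated SDs, an uncorrected RSB-FB test on that pooled SD has about 8.6% type I error instead of 5%. With Bonferroni it has 3.7% instead of 1.67%, so its apparent 24% power at 0.80 is partly bought with excess false positives.

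**6. Exactly one block significant against saline, RSB-FB not significant** (simulation, Bonferroni):

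| Scenario | Frequency |
|---|---|
| Identical blocks, 1.0 to 1.5 below saline | 23% to 34% |
| Identical blocks, 2.05 below saline | 5.6% (stated SDs) to 18% (common SD 2.1) |
| Planning means and stated SDs | about 8% |

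**The case against.** The strongest defence is that a direct, corrected RSB-FB test is already planned and that the Objectives section tells the reader which pair matters. The sentence quoted as primary comes from the sample-size paragraph; the analysis paragraph is generic to all quantitative variables, and nowhere is three-group significance called the criterion for success. Much of this stands. A reader might infer that the trial can say nothing about which block is better. That is true of the three-group result, not of the analysis as a whole: the contrast is undesignated, not absent.

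A reader might also infer that the plan intends to claim superiority because one block alone beats saline. No sentence proposes this. The pattern is common only when block effects are smaller (1.0 to 1.5 units) than both planning differences from control (2.45 and 1.65). Nor does it peak together with the near-certain three-group result: at 1.0 unit the three-group test is significant in only 38% to 55% of trials.

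At the planning means, 76% of simulated trials have a significant three-group test without a significant RSB-FB pair. The blocks truly differ by 0.80 there, so this figure mainly reflects low RSB-FB power and is not evidence about the decision rule.

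The defence does not explain why the only comparison in the objective should share its error rate with two comparisons that are not in it. A three-group test followed by all pairs suits a trial whose pairs are of equal interest.

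**Conclusion.** The concern holds as a mismatch between the objective and the designated comparison. On the plan's own figures, about 90% of the three-group signal is block against saline, and identical blocks 2.05 units below saline would give a significant result in about 95% to 99.7% of trials. That near-certainty depends on the size of the block effect and falls for smaller effects.

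The RSB-FB test is planned, but nothing makes it decisive. If Bonferroni covers the three pairs, the cost is a fall in power from 28% to 15% for 0.80 units, using the two groups' own variances. The result rests on normal scores at one time point and on the cited SDs.

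The documents do not support concluding that 23 per group is an arithmetical error: it reproduces for a three-group test. What cannot be sustained is reading its 80% as power for RSB versus FB.

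**What to change.** In STATISTICAL METHODS, state that:

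1. The primary comparison is RSB versus FB on the postoperative pain score, by a two-group test using those two groups' own variances (not the three-group pooled SD), two-sided at 0.05, reported as a difference with 95% CI.
2. Superiority of a block is concluded only from this comparison, not from the three-group test or from one block alone differing from control.
3. RSB versus control and FB versus control are secondary, with Bonferroni kept for these two (0.05/2 = 0.025 each). The three-group test is descriptive.
4. The 80% power refers to the three-group calculation. With 25 per arm the primary comparison has about 28% power for 0.80 units and 41% for one unit, and a non-significant result is not evidence of equivalence.

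The pain time point or summary must also be named, or the first item still leaves several candidate tests. The designation should be made before results by group are seen; after that it would have to be reported as post hoc.

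**Cost.** Wording only, with no extra patients or data. The control comparisons lose primary status, and a significant three-group test can no longer be presented as the primary success. The change also exposes the imprecision of the deciding contrast: the expected 95% CI half-width is about 2.01 × 0.566 = 1.14 units, wider than the 0.80 planning difference. Rewording cannot remove that.

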The time to first analgesia request analysis was done using the Kaplan-Meier method and comparison between groups was done using the log-rank test. The Coxregression method was used to calculate the hazard ratio (HR) for risk estimation with its 95% confidence interval (CI). All tests were two-tailed. A p-value < 0.05 was considered significant.

Source of funding:

Will be provided by Theodor Bilharz Research Institute.

Time plan:

Starting date: August 2017.

References:

- 1. Merskey H. Classification of chronic pain: description of chronic pain syndromes and definitions of pain terms. Monograph for the subcommittee on Taxonomy International Association for the study of pam. Pain Suppl Vol 3. Amsterdam: Elsevier Science 1986.
- 4. Sites BD and Brull R. Ultrasound guidance in peripheral regional anesthesia: philosophy, evidence-based medicine, and techniques. Current Opinion in

Anesthesiology; 19: 630-9. 2006.

- 5. Paul F. White. New Criteria for Fast-Tracking After Outpatient Anesthesia: A Comparison with the Modified Aldrete's Scoring System. Anesth Analgesia criteria for fast tracking;88:1069–72. 1999.
- 6. Charlton S GJ. Cochrane Database of Systematic Reviews Perioperative transversus abdominis plane (TAP) blocks for analgesia after abdominal surgery (Review) Perioperative transversus abdominis plane (TAP) blocks for analgesia after abdominal surgery (Review). Cochrane Database Syst Rev Art. 2010;(12):1–59.
- 7. Flack SH, Martin LD, Walker BJ et al. Flack abstract. Available from: http://www2.pedsanesthesia.org/meetings/2011winter/syllabus/submissions/abstract s/wapd/GA30.pdf.

Research Template 12 Final Version: 14/11/2011

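### The stated 80% power for one unit at 23 per group does not hold for rectus sheath block versus field block, where it is about 38%

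*Combined protocol and SAP*

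**What the plan says.** The Objectives section sets the question as a contrast between the two blocks: "To compare between Ultra-sound guided rectus sheath block VS Field block infiltration in providing a good analgesia", with the aim of finding which is superior. Postoperative pain is the primary outcome.

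The sample size paragraph under STATISTICAL METHODS takes planning values from earlier publications: "postoperative pain score in RSB group was 4.65 ± 2.1 , while in local infiltration group it was 5.45 ± 1.9", and 7.1 with SD 1.1 for control. It then states that "a sample size of 23 in each group will be able to detect a one unit difference between the groups with 80% power", by one-way ANOVA in G*Power with alpha set to 0.05. It continues: "To allow for drop-outs, 25 patients in each group were recruited".

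It does not say which three means, which common SD or which effect size f was entered. It gives no power for any pair of groups.

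The analysis paragraphs that follow plan a three-group ANOVA (or Kruskal-Wallis) and then an unnamed post-hoc test for pairs. On multiplicity they say "Due to multiple comparisons, the p-value was corrected using the Bonferroni method", without giving the number of comparisons.

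**The concern.** An ANOVA power figure has a meaning only for a stated set of means and a stated SD. Without them, a reader will take one unit between the groups as one unit between any two of them, and will apply the 80% to RSB versus FB because that is the stated objective. With SDs near 2 and 23 per group, 80% power for one unit between two groups is not plausible on its face.

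The risk lies in interpretation. If RSB and FB do not differ significantly, a stated 80% would make that look like fair evidence that they are within a unit of each other. If the true power is far lower, it is no such evidence.

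**Working it through.** **Inputs (STATISTICAL METHODS).** Means 4.65 (RSB), 5.45 (FB), 7.1 (control); SDs 2.1, 1.9, 1.1; 23 evaluable per group, 25 recruited; alpha 0.05, two-sided. Assumptions: the common SD entered (not stated; 1.1 to 2.1 tried) and three pairs for Bonferroni (0.05/3).

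**1. Reproducing 23.** Overall ANOVA power comes from the noncentral F with λ = n·Σ(μᵢ − μ̄)²/SD² and df 2 and 3n − 3. For means 0, 1, 2 the sum of squares is 2. With SD 2.1 (variance 4.41):

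- n = 22: λ = 22 × 2/4.41 = 9.98, power 79.5%
- n = 23: λ = 23 × 2/4.41 = 10.43, power 81.4%

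So 23 is the smallest size reaching 80%. The same pattern needs 19 per group at SD 1.9, 16 at the three-group pooled SD of 1.754, and 15 at the average SD of 1.70. The plan's quoted means need only 10 to 15 per group for SDs of 1.70 to 2.1, so they were not the direct input.

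**2. If one unit is the largest gap among the three means.** Overall ANOVA power at n = 23:

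| Common SD | Means 0, 0.5, 1 | Means 0, 0, 1 |
|---|---|---|
| 2.1 | 27.3% | 35.2% |
| 1.754 | 37.6% | 48.3% |
| 1.70 | 39.7% | 51.0% |
| 1.1 | 77.5% | 88.6% |

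Power is near or above 80% only if the control SD of 1.1 is used for every group. At SD 1.1 the means 0, 0.25, 1 also return 23 (78.9% at 22, 80.9% at 23).

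**3. Pairs, one unit, n = 23.** Two-sided t test, df 44, noncentrality δ = (d/SD)·√(n/2), where √(23/2) = 3.391 and SD is the root mean of the two variances. Critical t is 2.015 at 0.05 and 2.489 at 0.05/3.

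| Pair | SD | δ | Power at 0.05 | Power at 0.05/3 |
|---|---|---|---|---|
| RSB–FB | √((4.41 + 3.61)/2) = 2.002 | 1.693 | 38.1% | 22.5% |
| RSB–control | √((4.41 + 1.21)/2) = 1.676 | 2.023 | 50.8% | 33.1% |
| FB–control | √((3.61 + 1.21)/2) = 1.552 | 2.184 | 57.0% | 39.0% |

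A simulation of the Welch test with the unequal SDs (200,000 runs, alpha 0.05) gave 37.9%, 50.2% and 56.4%.

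**4. RSB–FB in more detail.**

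- With no drop-outs (n = 25): 40.9% for one unit (24.8% at 0.05/3).
- Difference detectable with 80% power: 1.69 units at n = 23 (1.98 at 0.05/3); 1.62 at n = 25 (1.89).
- Size needed for 80% power on one unit: 64 per group (86 at 0.05/3).
- Under the reading in step 1 (SD 2.1), an adjacent one-unit pair has 35% power (20% at 0.05/3).

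**5. At the plan's quoted gaps, n = 23, alpha 0.05.** RSB–control (7.1 − 4.65 = 2.45): 99.8%. FB–control (7.1 − 5.45 = 1.65): 94%. RSB–FB (5.45 − 4.65 = 0.8): 26%.

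**The case against.** The best defence is that the sentence is an overall ANOVA statement and is true as such. It names the test, and for three groups a one-unit difference can mean successive groups one unit apart, which is the pattern that returns 23. On that view nothing was miscalculated and the fault is incomplete reporting. This stands in part: 23 need not be a wrong number. But the sentence does not say that the means span two units, and a significant overall F can come from the control group alone, so it does not show which block is better.

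The reconstruction is also not unique, since a one-unit span with SD 1.1 can return 23. That is fair. However, 1.1 is the control SD, and the plan gives 2.1 and 1.9 for the two blocks.

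The 38% also depends on method. If the post-hoc test uses the three-group error term (SD 1.754, 66 df), RSB–FB power for one unit is 48% at 23 and 51% at 25, with a detectable difference of 1.47 units at 23. With three-pair Bonferroni the powers are 31% and 34%, and the detectable difference at 23 is 1.71. This too is fair, and it means that a flat claim that a one-unit difference would more often be missed than found fails in one case: unadjusted, full enrolment, pooled error. But 1.754 understates the spread in this pair (2.002), and every variant is far below 80%.

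Finally, the trial is well powered against control at the quoted means. That is correct, but it does not help the comparison in the Objectives.

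**Conclusion.** The concern holds. As an unqualified statement, 80% power for one unit at 23 per group is not delivered for any pair on the plan's own SDs. For RSB versus FB it is about 38%, some 42 percentage points below the stated figure, and about 23% after Bonferroni over three pairs. The 38% rests on SDs of 2.1 and 1.9, a two-group t test, alpha 0.05 two-sided and 23 evaluable per group. A pooled three-group error term raises it to 48% and full retention to 41%; both together give 51%.

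That the 80% came from means 0, 1, 2 with SD 2.1 is an inference from the exact match on 23. The shortfall for RSB versus FB does not depend on it. This corrects a stated power rather than asking for extra detail, and it should be corrected before results are interpreted.

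**What to change.** Keep 75 patients and rewrite the sample size paragraph.

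- State the three means and the common SD entered in G*Power, and describe the 80% as overall ANOVA power for that pattern. If it was 0, 1, 2 with SD 2.1, say that it applies when the group means span two units.
- Remove the unqualified one-unit claim.
- Add, for example: *23 evaluable patients per group give 80% power for an RSB versus field block difference of about 1.7 VAS units (SDs 2.1 and 1.9, two-sided alpha 0.05, two-group t test), and about 38% power for a difference of one unit.*
- Name the post-hoc test and state how many pairwise comparisons Bonferroni covers. If three, add about 2.0 units and 23%. If the test uses the three-group error term, recompute the figures on that basis.

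The cost is one reworded paragraph and a less favourable stated figure. No patients are added and the analysis does not change. Raising the power for one unit to 80% in this pair would take 64 per group; that is given for scale and is not being asked for.
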